#### **10.3.2.2.2 Secondary Endpoints**

##### **10.3.2.2.2.1 Depth of Platelet Nadir**

The first secondary endpoint is the depth of platelet nadir from the start of the first on-study chemotherapy cycle through the EOTP. Linear regression models will be used to compare the mean nadir between the romiplostim and placebo groups. Dependent variables will include the treatment group, the stratification factor of tumor type and baseline platelet count, and the interactions between treatment group and the stratification factors. The normality assumption for linear regression models will be

checked using a normal probability plot of the residuals and the Shapiro-Wilk test (Shapiro and Wilk, 1965). If the data fail to meet the normality assumption, data transformation or a non-parametric method may be considered. The detailed analysis plan will be described in the Statistical Analysis Plan.

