4.1 Planned Covariates

The following baseline characteristics are specified as potential confounding covariates:

- Stratification factor of tumor type (Gastrointestinal, **Pancreatic**, Colorectal) Stratification factor of baseline platelet count ($< 50 \times 10^9/L$, $\geq 50 \times 10^9/L$)
- Age (continuous and categorized ≤ 65 years, > 65 years)
- Sex (Male, Female)
- Race (White, Black or African American, Asian, American Indian or Alaska Native, Other)
- Ethnicity (Hispanic or Latino, Not Hispanic or Latino)
- Region (United States, Europe, Rest of World)
- Body mass index
- ECOG (0–1, ≥ 2)
- Stage of disease (Stage 1 to 3, Stage 4 or recurrent disease)
- Line of chemotherapy treatment (1, ≥ 2)
- **Type of chemotherapy regimen (FOLFOX, FOLFIRINOX, FOLFOXIRI, CAPEOX)**
- Number of previous chemotherapy cycles (≤ 2 , > 2)
- Prior or Concurrent Bevacizumab use (Yes, No)
- Baseline platelet count (continuous)
- Prior bleeding events (Yes, No)

- Prior platelet transfusions (Yes, No)
- Prior use of erythropoiesis-stimulating agent (Yes, No)
- Prior use of granulocyte colony-stimulating factor (Yes, No)
- Prior use of programmed cell death 1 inhibitors or programmed cell death ligand 1 inhibitors (Yes, No)
- Concurrent use of programmed cell death 1 inhibitors or programmed cell death ligand 1 inhibitors (Yes, No)

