9.1 General Considerations

Continuous variables will be summarized descriptively by the n, mean, standard deviation, median, Q1 (25th percentile), Q3 (75th percentile), minimum, and maximum. The confidence interval and standard error for the mean will also be summarized for efficacy variables that are continuous. Categorical variables will be summarized descriptively by the number and percentage in each category. Missing values will be shown as a separate category. The confidence interval will also be summarized for dichotomous efficacy variables.

Time to event variables will be summarized with hazard ratios, Kaplan-Meier curves, Kaplan-Meier quartiles, the number of subjects at risk, the number of subjects censored, and the number of subjects with events.

Where confidence intervals are provided, these will be 2-sided at the 95% level, unless otherwise specified.

The primary efficacy endpoint will be compared between the romiplostim and placebo groups at the significance level of 0.05 using a 2-sided test. If statistical significance is achieved for the primary endpoint in favor of romiplostim, **the following secondary efficacy endpoints will be tested using a fixed sequence hierarchical testing procedure to control the family-wise Type I error rate below 2-sided 0.05 level. The family of hypotheses is ordered as follows:**

- the depth of platelet count nadir from the start of the first on-study chemotherapy cycle through the end of the treatment period
- the time to first platelet response, defined by platelet count $\geq 100 \times 10^9/L$, in the absence of platelet transfusions during the preceding 7 days.
- the duration-adjusted event rate of \geq grade 2 bleeding events as assessed per CTCAE version 5.0 grading scale
- overall survival
- platelet transfusion(s) during the treatment period
- achieving platelet count $\geq 100 \times 10^9/L$ at any time after study day 1 to week 4 (ie, 7 days after the planned third dose of investigational product) in the absence of platelet transfusions during the preceding 7 days

Starting with the hypothesis of platelet count nadir, if any null hypothesis in the sequence is rejected at a 2-sided significance level of 0.05, then the subsequent hypothesis will be tested; if any null hypothesis is accepted, then the subsequent hypotheses will not be tested.

Summary statistics without formal testing will be provided for other endpoints.

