9.4 Demographic and Baseline Characteristics

The following demographics and baseline characteristics will be summarized by treatment group and overall using descriptive statistics for the FAS.

- The stratification factor of tumor type (gastrointestinal, **pancreatic**, colorectal)
- The stratification factor of baseline platelet count ($< 50 \times 10^9/L$, $\geq 50 \times 10^9/L$)
- Age (continuous and categorized ≤ 65 years, > 65 years)
- Sex (Male, Female)
- Race (White, Black or African American, Asian, American Indian or Alaska Native, Native Hawaiian or Other Pacific Islander, Other)
- Ethnicity (Hispanic or Latino, Not Hispanic or Latino)
- Region (United States, Europe, Rest of World)
- Body mass index
- Weight
- Height
- ECOG (0-1, ≥ 2)
- Stage of disease (Stage 3, Stage 4 or recurrent disease)
- Line of chemotherapy treatment (< 2 , ≥ 2)
- **Type of chemotherapy regimen (FOLFOX, FOLFIRINOX, FOLFOXIRI, CAPEOX)**
- Number of previous chemotherapy cycles (≤ 2 , > 2)
- Dose of previous chemotherapy cycle before entering the study (Modified dose, Full dose)
- Prior or Concurrent Bevacizumab use (Yes, No)
- Baseline platelet count (continuous and categorized by CTCAE version 5.0 thrombocytopenia grade)
- Prior bleeding events (Yes, No)

- Prior platelet transfusions (Yes, No)
- Prior use of erythropoiesis-stimulating agent (Yes, No)
- Prior use of granulocyte colony-stimulating factor (Yes, No)
- Prior use of programmed cell death 1 inhibitors or programmed cell death ligand 1 inhibitors (Yes, No)
- Concurrent use of programmed cell death 1 inhibitors or programmed cell death ligand 1 inhibitors (Yes, No)

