9.5.1 Analyses of Primary Efficacy Endpoint(s)

The primary endpoint is the proportion of subjects with no thrombocytopenia induced dose modification. **The primary analysis will be based on the adjudication committee (AC) assessment of thrombocytopenia-induced dose modification. The proportion along with a 95% CI will be provided for each treatment group.** A 2-sided CMH test will be used to compare groups controlling for the stratification factors of tumor type and baseline platelet count. The Mantel-Haenszel estimate of common odds ratio for romiplostim vs placebo will be estimated along with a 95% CI for each treatment group and the difference in proportions between treatment groups will be provided with a 95% CI.

For primary analysis, subjects with missing observations for cycle 2 and/or cycle 3, or who discontinued any myelosuppressive agent early, are considered as not meeting the criteria of the primary endpoint. The following sensitivity analyses will be explored:

A sensitivity analysis using the investigator's assessment on thrombocytopenia -induced dose modification will be performed. The number and percentage of subjects with concordant and discordant assessments per investigator and AC will be summarized.

If more than 10% of subjects in the full analysis set have COVID-19 related IPDs with missing chemotherapy without platelet count assessment for cycle 2 or cycle 3, a sensitivity analyses may be explored by excluding those subjects with COVID-19 related IPDs.

For each specified covariate in [Section 4.1](#), sensitivity analyses will be conducted to evaluate any potential confounding: (1) a 2-sided CMH test checking conditional independence between treatment groups and primary endpoint outcomes controlling for each individual covariate, (2) a logistic regression with primary endpoint outcome as the dependent variable and explanatory variables from treatment group, the specified covariate, and interaction of treatment by covariate.

Subgroup exploratory analyses will also be performed to explore the consistency of the treatment effect between subgroups described in [Section 4.2](#). FAS will be used for the primary endpoint analysis.

9.5.2 Analyses of Secondary Efficacy Endpoint(s)**9.5.2.1 Depth of Platelet Count Nadir From the Start of the First On-study Chemotherapy Cycle Through the EOTP (1)**

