The depth of platelet count nadir after the start of the 1st on-study chemotherapy cycle through the EOTP will be summarized and compared between romiplostim and placebo group. Summary statistics will include n, mean, standard deviation, standard error, median, Q1, Q3, minimum, and maximum. Linear regression models will be used to compare the mean nadir between the romiplostim and placebo groups. Dependent variables will include the treatment group, the stratification factors of tumor type and baseline platelet count, and the interactions between treatment group and the stratification factor. FAS will be used for the all the secondary endpoint analyses.

The following sensitivity analyses will be explored for the endpoint if subjects never started the first on-study chemotherapy cycle or never have platelet count measured after the first on-study chemotherapy cycle:

- (1)** Impute platelet nadir using the lowest nadir value for the remaining subjects in the treatment group
- (2)** Impute platelet nadir using the lowest platelet count from baseline to the last platelet count assessment
- (3)** Impute platelet nadir using the mean nadir value for the treatment group
- (4)** Sensitivity analysis excluding the missing subjects

The normality assumption for linear regression models will be checked using a normal probability plot of the residuals and the Shapiro-Wilk (SK) test ([Shapiro and Wilk 1965](#)).

The following steps will then take place:

If the normal probability plot and the SK test show strong evidence against the normality assumption, log-transformation will be conducted. After the transformation, the normality will be checked again using the normal probability plot of the residuals and the SK test:

- a. If the normality assumption holds after the log-transformation, linear regression models will be used on log-transformed variables to compare the mean nadir.
- b. If the normality assumption does not hold after the log-transformation, the nonparametric van Elteren test will be used to compare the mean nadir.

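### The platelet nadir model, first gate of the secondary sequence, includes treatment-by-stratum interactions but names no treatment contrast or weighting for its p-value

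*SAP*

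**What the plan says.** SAP 9.5.2.1 sets the aim: "Linear regression models will be used to compare the mean nadir between the romiplostim and placebo groups". The model terms are treatment group, "the stratification factors of tumor type and baseline platelet count, and the interactions between treatment group and the stratification factor". Protocol 10.3.2.2.2.1 gives the same model, ends the sentence in the plural ("stratification factors. The normality assumption for linear regression models will be") and leaves the detail to the SAP. Neither document names LS-means, a contrast, a factor coding or stratum weights.

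If normality still fails after log-transformation, SAP 9.5.2.1 says "the nonparametric van Elteren test will be used to compare the mean nadir".

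SAP 9.1 tests the secondary endpoints in a fixed order at 2-sided 0.05, "Starting with the hypothesis of platelet count nadir", and stops at the first hypothesis that is not rejected.

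The stratification factors are tumor type (three levels) and baseline platelet count (below 50, or 50 and above, x 10^9/L). Platelet count enters the nadir model only as this two-level factor. The continuous count is on the covariate list in SAP 4.1 and is summarised under SAP 9.4. For each listed covariate SAP 9.5.1 promises that "sensitivity analyses will be conducted to evaluate any potential confounding", but only for the primary endpoint.

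**The concern.** Once treatment interacts with the strata, the model has no single treatment effect. It has stratum-specific effects, and a p-value comparing the arms exists only after someone chooses how to average them. Two statisticians could both follow SAP 9.5.2.1 and report different p-values. If the effects differ between strata, their estimates would differ too.

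The other secondary analyses do not have this gap. The stratified log-rank tests, the stratified Andersen-Gill model and the CMH tests each give one treatment comparison. The gap falls on the endpoint that opens the sequence: if nadir fails, time to platelet response, bleeding rate, overall survival, transfusion and week-4 response are not formally tested.

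A second, smaller point is that dichotomising the baseline count discards information on a variable that is already collected and plausibly related to nadir.

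**Working it through.** **Inputs from the documents.** N = 162, allocated 108 to 54; 3 x 2 strata; 2-sided 0.05. No SD, effect size, stratum shares or power are given for nadir, so there is no nadir figure to reproduce. The one stated power, 93% for the primary endpoint, does reproduce. The plan's formula gives 0.237 against 0.528 (odds ratio 3.60), and power is 93.4-93.7% with continuity correction or 95.7% without.

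**Assumptions.** Tumor mix (gastrointestinal/pancreatic/colorectal) 20/15/65, 30/30/40 or equal thirds. Share below 50: 10, 20, 30 or 50%. Tumor type and platelet category independent, 2:1 allocation within every stratum, the same effect in all strata, and both interactions in the model. Pancreatic cancer entered only at Amendment 5, which is a reason not to presume equal thirds, but no share is stated.

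**Standard error.** The main-effects SE in SD units is sqrt(1/108 + 1/54) = 0.1667. For tumor shares p_i with contrast weights w_i, and platelet shares q_j with weights v_j, the variance ratio to main effects is

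1 + (sum of w_i^2/p_i - 1) + (sum of v_j^2/q_j - 1).

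- Observed-proportion weights (w = p, v = q): both brackets are zero, so the ratio is 1.00 in every setting.
- Equal weights, 20/15/65 with 20% below 50: the tumor sum is (1/9)(1/0.20 + 1/0.15 + 1/0.65) = 1.467 and the platelet sum is (1/4)(1/0.2 + 1/0.8) = 1.5625. The variance ratio is 1 + 0.467 + 0.5625 = 2.03, and the SE ratio is 1.42.
- Equal weights, thirds with 30% below 50: the tumor sum is 1 and the platelet sum is (1/4)(1/0.3 + 1/0.7) = 1.19. The SE ratio is 1.09.
- Equal weights, thirds with 50% below 50: both sums are 1. The SE ratio is 1.00.
- Over all the assumed mixes the equal-weight SE ratio runs from 1.00 to 1.80.

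**Power from an assumed 90%.** Power = Phi((1.28 + 1.96)/ratio - 1.96). A ratio of 1.42 gives 62%, 1.09 gives 84%, 1.00 gives 90% and 1.80 gives 44%.

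**Power by assumed effect size.** Power = Phi(d/(ratio x 0.1667) - 1.96).

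| Effect (SD) | Main effects or observed weights | Equal weights, ratio 1.42 | Equal weights, ratio 1.80 |
|---|---|---|---|
| 0.5 | 85% | 56% | 38.5% |
| 0.8 | 99.8% | 92% | 76% |
| 1.0 | 100% | 98.8% | 91.5% |

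**Simulation check** (effect 0.54 SD, 20/15/65 with 20% below 50, both interactions). Equal-weight power was 57-61%, depending on the allocation scheme. Over all common-effect settings simulated, main-effects and observed-proportion power was 86-91%. Type I error was 4.7-5.2%.

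**Unequal effects.** Let the effect be a at 50 and above and b below 50, with share s below 50. Equal weighting breaks even when (0.5a + 0.5b)/ratio = (1 - s)a + s*b. For thirds with s = 0.2 the ratio is 1.25, so 0.4a + 0.4b = 0.8a + 0.2b and b = 2a. With 10-30% below 50, the break-even over the assumed mixes is about 1.5 to 3.5 times.

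**Continuous baseline count.** Adding it to the two-level factor multiplies residual variance by (1 - rho^2)/(1 - rho^2 R^2). Here rho is the baseline-nadir correlation and R^2 is the share of baseline variance that the factor explains (0.33 to 0.69 under three assumed distributions). With rho = 0.6 and R^2 = 0.33, the ratio is 0.64/0.881 = 0.726 and the SE ratio is 0.852. Power is Phi(3.24/0.852 - 1.96) = 96.7%, a gain of 6.7 points. With rho = 0.2 and R^2 = 0.69, the gain is 0.4 points.

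**The case against.** The strongest reply is that nothing in the plan is wrong. Equal weighting is a legitimate target that does not depend on enrolment mix, and any rule fixed in advance controls type I error. Nadir is reached only if the primary endpoint succeeds, so the drug is then likely to be raising platelets substantially. At 0.8 to 1.0 SD a ratio of 1.42 still leaves 92-98.8% power. If the residuals are not normal, the van Elteren test applies and the question disappears. Every loss shown rests on assumed shares. Equal weighting can even win: in simulation with thirds and 20% below 50, it had 95% power against 90% when the effect below 50 was three times larger. All of this stands, and it limits the size of the point. It does not supply the missing contrast. The same simulation with no effect below 50 gave 36% against 90%, so the choice can matter in either direction.

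The continuous covariate can fairly be called a design preference. Leaving it out contradicts nothing in the documents.

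A reader might infer from the singular in the SAP and the plural in the protocol that the two documents specify different interactions. They do not show that. Both speak of interactions in the plural, and the protocol uses the singular for both factors earlier in the same sentence. SAP 9.2 also uses the singular loosely, and SAP Section 10 declares no departure from the protocol. A reader might also take the bare treatment coefficient from reference-cell coding as the test, where the loss would be larger. The stated aim of comparing group means does not support that reading.

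**Conclusion.** The point holds as a gap in pre-specification. The p-value for the first secondary gate is not uniquely defined, because the model contains treatment interactions and no averaging rule. No error in a stated figure and no threat to type I error is shown.

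The size is conditional. With both interactions and a common effect, equal weighting turns an assumed 90% power into anything from 44% to 90% over the assumed mixes. The example mix gives 62%, and fully balanced strata give no loss. Observed-proportion weighting or a main-effects model gives up nothing. If the effect is near 1 SD, or the van Elteren fallback is used, little or nothing is at stake. Because the documents give no stratum shares, SD or effect size for nadir, no single loss can be claimed. The difference between singular and plural is a wording matter only. The point should be acted on because five endpoints depend on the test and the remedy is nearly free.

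**What to change.** Before unblinding, amend SAP 9.5.2.1:

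- State that the p-value and 95% CI, on the original and log scales, come from the treatment contrast weighted to observed stratum proportions. Alternatively, use a main-effects model and keep the interactions as an exploratory consistency check. If equal weighting is the intended target, say so explicitly and accept the possible loss.
- Add continuous baseline platelet count as a covariate in the linear model. The gain depends on its unknown correlation with nadir.
- As a tidy-up, write the interaction phrase with factors in the plural.

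The observed-proportion contrast keeps the protocol model and costs one or two sentences. A main-effects model or the added covariate also needs an entry in SAP Section 10, which now declares no changes. No new data are needed, and the van Elteren fallback can stay as written.

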3.2 Sample Size

A sample size of 162 is chosen with 2:1 randomization ratio (108 romiplostim, 54 placebo), stratified by tumor type (**Gastrointestinal, Pancreatic, and Colorectal**) and baseline platelet count ($< 50 \times 10^9/L$, $\geq 50 \times 10^9/L$). In two small studies ([Al Samkari et al, 2018](#); [Soff et al, 2017](#)), few patients with CIT spontaneously recovered their platelet counts to adequate levels: 5 of 22 (23%) and 1 of 8 (13%), respectively. A phase 2 study showed 75% (24 out 32 subjects) subjects resumed chemotherapy after treatment with romiplostim ([Soff et al, 2017](#)). From retrospective reviews, between 65% (13 of 20 subjects) and 82% (18 of 22 subjects) subjects did not have any thrombocytopenia-induced chemotherapy dose modifications after treatment with romiplostim ([Parameswaran et al, 2014](#); [Al-Samkari et al, 2018](#)).

Thrombocytopenia-induced chemotherapy dose modifications in one cycle may be correlated with the previous cycle outcome. Assume that p is the probability of receiving a planned on-study chemotherapy regimen with no thrombocytopenia-induced chemotherapy dose modifications in a cycle, ρ is the cycle correlation and the correlation is the same in romiplostim group and control group, the probability of receiving the planned chemotherapy regimen with no thrombocytopenia-induced chemotherapy dose modifications in two subsequent cycles, $p_{2,3}$ for Cycle 2 and 3, can be calculated as $p_{2,3} = p^2 + \rho p(1 - p)$.

A higher cycle correlation is shown to be associated with a lower odds ratio of treatment effect for romiplostim vs control ([Figure 3-1](#)).

Figure 3-1. Relationship Between Cycle Correlation and Treatment Effect^a

^a Assume 30% and 60% probability of having no dose modifications in one cycle for placebo and romiplostim respectively.

From conservative considerations, probability of receiving the planned on-study chemotherapy regimen with no thrombocytopenia-induced chemotherapy dose modifications in one cycle for subjects treated in placebo group and romiplostim group is assumed to be 30% and 60% respectively, with a strong cycle correlation of 0.7 between two subsequent cycles. The odds ratio of having no thrombocytopenia-induced chemotherapy dose modifications in two cycles for romiplostim vs placebo is 3.6 ([Figure 3-1](#)).

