The chosen sample size of 162 (108 romiplostim, 54 placebo) will provide 93% power to detect the treatment effect between the romiplostim group and the placebo group as defined in the

primary endpoint at a two-sided significance level of 0.05 using a Cochran-Mantel-Haenszel (CMH) test. Power calculations were performed in East version 6.4 using a 2-sided CMH test at significance level of 0.05 and stratification by tumor type and baseline platelet count ($< 50 \times 10^9/L$, $\geq 50 \times 10^9/L$).

One interim analysis will be performed at approximately 81 subjects (50% of the planned sample size) completing three cycles of chemotherapy. The non-binding futility boundary is constructed using Lan-DeMets spending function with the O'Brien-Fleming approach. Assuming an observed 35% of subjects in the control arm with no thrombocytopenia-induced chemotherapy dose modification in one cycle, the power is estimated to be 84% at the interim analysis and the probability of stopping for futility is 2%.

4. Covariates and Subgroups

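### Nadir sensitivity analysis (3) fills missing values with the treatment-group mean, so it nearly repeats exclusion (4) with a standard error that is too small

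*SAP*

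**What the plan says.** Depth of platelet nadir is the first secondary endpoint in the fixed testing sequence (SAP 9.1). The main rule for a missing value is in SAP section 5: a subject who never starts the first on-study cycle, or has no platelet count after it, is given the baseline count.

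SAP 9.5.2.1 compares arms by linear regression with treatment, the stratification factors and their interactions. It then lists four sensitivity analyses to be explored for the same subjects:

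- (1) "Impute platelet nadir using the lowest nadir value for the remaining subjects in the treatment group"
- (2) the subject's own lowest count from baseline to the last assessment
- (3) "Impute platelet nadir using the mean nadir value for the treatment group"
- (4) "Sensitivity analysis excluding the missing subjects"

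No multiple imputation or variance correction is described for (3). Neither document gives a rate of missing nadirs or a standard deviation for the nadir. SAP 8.4 says only that earlier dropout on placebo is possible.

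**The concern.** Placing every missing subject exactly at the arm mean leaves the arm mean where it was. It also enlarges the apparent sample and adds no spread. The analysis therefore returns the answer of the exclusion analysis with more apparent precision than the data hold.

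Both analyses rest on the same assumption, that subjects without a nadir resemble those in their arm who have one. For some of them this is doubtful: under Protocol 7.4.1.2, a subject who has not started cycle 1 after 12 weeks of investigational product is classed as a non-responder.

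What is at stake is how the robustness results are read. If (3) and (4) are tabulated as two separate checks, (3) looks like further and firmer support for the main result, which it is not.

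**Working it through.** **Inputs.** Arm sizes: "A sample size of 162 is chosen with 2:1 randomization ratio (108 romiplostim, 54 placebo" (SAP 3.2). Test: "at the significance level of 0.05 using a 2-sided test" (SAP 9.1). Missing fraction: assumed, 5% to 30%. SD of the nadir: not stated. It cancels in the unadjusted check and is set to 25 in the adjusted one.

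**The plan's own figure.** No power is stated for the nadir. As a check on the arm sizes, the primary-endpoint power can be reproduced. The per-cycle rate "is assumed to be 30% and 60% respectively, with a strong cycle correlation of 0.7 between two subsequent cycles", so with p² + ρp(1 − p):

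- placebo: 0.09 + 0.7 × 0.21 = 0.237
- romiplostim: 0.36 + 0.7 × 0.24 = 0.528
- odds ratio: (0.528/0.472)/(0.237/0.763) = 3.60, against the stated 3.6
- power of a Wald test on the log odds ratio with 108 and 54 subjects: 92.9%, against the stated 93%

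**Step 1: one arm, no covariates.** Let n be randomized, m the missing fraction and s the SD.

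- Exclusion: SE = s/√(n(1 − m)).
- Arm-mean fill: the sum of squares is unchanged but is spread over n subjects, so the apparent SD is about s√(1 − m) and SE = s√(1 − m)/√n.
- Ratio of the second to the first: 1 − m. The arm means, and so the arm difference, are identical.

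**Step 2: both arms, pooled variance.** With k1 and k0 subjects observed, the ratio is √((k1 + k0 − 2)/160) × √(1/108 + 1/54) divided by √(1/k1 + 1/k0). At 10% missing (97 and 49): √(144/160) × 0.1667 = 0.1581, divided by 0.1753, gives 0.902. The true size of the nominal 5% test is 2(1 − Φ(1.96 × ratio)).

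| Missing per arm | Observed (romiplostim/placebo) | SE ratio, (3) to (4) | True size of (3) |
|---|---|---|---|
| 5% | 103/51 | 0.949 | 6.3% |
| 10% | 97/49 | 0.902 | 7.7% |
| 20% | 86/43 | 0.795 | 11.9% |
| 30% | 76/38 | 0.702 | 16.9% |

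**Step 3: simulation without covariates, no effect.** Rejection rates for (3) were 6.2% (5% missing in both arms), 7.6% (10% in both), 9.9% (10% romiplostim, 20% placebo), 11.7% (20% in both) and 13.1% (15% romiplostim, 30% placebo). Exclusion gave about 5%. A second, separate simulation gave 6.3%, 7.6%, 9.8%, 11.7% and 12.8%.

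**Step 4: simulation of the covariate-adjusted model, no effect** (4,000 trials per row, SD 25, assumed stratum shares).

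| Missing per arm | Interactions | Mean SE (4) | Mean SE (3) | Actual SD of estimate (3) | Rejects (4) | Rejects (3) |
|---|---|---|---|---|---|---|
| 10% | no | 4.43 | 4.00 | 4.55 | 5.8% | 8.9% |
| 10% | yes | 4.48 | 4.03 | 4.43 | 4.4% | 7.2% |
| 20% | no | 4.72 | 3.78 | 4.62 | 4.7% | 10.6% |
| 20% | yes | 4.76 | 3.80 | 4.74 | 5.1% | 10.8% |
| 30% | no | 5.05 | 3.54 | 5.06 | 5.2% | 16.8% |

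At 20% missing, the estimates from (3) and (4) differ by 0.55 to 0.65 on average in absolute value, against a standard error of about 4.7. They are nearly the same estimate. The standard error reported by (3) is about 3.8, while the estimate actually varies with an SD of 4.6 to 4.7.

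**The case against.** The strongest reply is that nothing confirmatory depends on (3). The gated test uses the baseline count, a rule that is the same in both arms, and the four analyses are exploratory. Analysis (4) sits beside (3) with a valid standard error, so a careful reader can see the discrepancy. The missing rate may also be low: platelets are counted weekly, and chemotherapy may start from week 4 even below 100 × 10⁹/L. All of this stands and limits the weight of the point. None of it makes the interval from (3) correct.

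A reader might infer more than the documents support:

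- **That (3) always looks stronger than (4).** This is exact only without covariates. In a simulated model with treatment and strata and no effect, (3) gave the larger p-value in 29% of trials at 5% missing in both arms and in 23% at 10%. The understatement holds on average. The 1 − m factor also does not carry over to the van Elteren test that SAP 9.5.2.1 names as a fallback.
- **That analysis (1) penalises romiplostim because that arm is larger.** With equal spread, equal missing fractions and no effect, the expected minimum is −2.50 SD among 97 subjects and −2.24 SD among 49. At 10% missing this moves the arm difference by only about 0.026 SD. The total penalty reverses if placebo has somewhat more missing data, the direction that SAP 8.4 anticipates: at 10% romiplostim and 12% placebo it is 0.250 against 0.268 SD.
- **That no listed analysis tests an unfavourable case.** Analysis (2) does so, subject by subject, with the same rule in both arms.

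**Conclusion.** The point holds for analysis (3) alone and is minor. As written, (3) reproduces the exclusion estimate, exactly without covariates and nearly so in the planned model, and understates its standard error by roughly 1 − m. Over an assumed 5% to 20% missing per arm, a nominal 5% test rejects about 6% to 12% of the time with no effect, and about 13% at 15% romiplostim and 30% placebo. Exclusion stays near 5%. These sizes rest on assumed missing fractions, normally distributed data and, in the adjusted model, assumed stratum shares. They also read the treatment group in (3) as the subject's own arm, which is the natural reading.

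It would be wrong to read these rates as the type I error of the gated nadir test. That test uses the baseline count and is untouched. The consequence is confined to the robustness evidence.

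**What to change.** Replace (3) in SAP 9.5.2.1 by multiple imputation of the missing nadir within each arm, from baseline platelet count (continuous), tumor type and platelet stratum, with results combined by Rubin's rules. The by-arm version keeps the idea behind (3), that a missing subject resembles comparable subjects in the same arm, and carries the imputation uncertainty into the interval. Optionally add a version with both arms imputed from the placebo model, which tests a different and less favourable assumption for romiplostim. Analyses (1), (2) and (4) need no change on this account.

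The cost is a few lines of SAP text, modest programming and wider confidence intervals for this sensitivity analysis. The main nadir analysis and the testing sequence do not change.
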